1.5 Sample Size

The planned sample size for this trial is 800 randomized and treated subjects. These subjects will be allocated into 4 treatment groups in a 1:1:1:1 ratio. Pair-wise testing of each ALD403 group vs. placebo will be performed. Two hundred subjects per group provides at least 95% power for each change in frequency of migraine days (Weeks 1-12) test individually assuming a treatment effect of at least 1 day and a common standard deviation of 2.7 days or less. Ninety percent power is retained for standard deviations up to 3 days. For the key secondary 75% responder

rates endpoints 95% power is achieved for the pair-wise comparisons assuming rates of 24% for placebo and 42% for ALD403. For the 50% responder rate endpoints 95% power is achieved for the pair-wise comparisons assuming rates of 50% for placebo and 68% for ALD403. For the percentage of subjects with a migraine on the day after dosing endpoint, 95% power is achieved for pair-wise comparisons assuming rates of 15% for placebo and 4% for ALD403.

These sample size calculations have been performed using Pass 2008 and are based upon t-tests and Chi-squared tests that should approximate the ANCOVA and CMH tests, respectively.⁴

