2.2 Clinical Trial Endpoints

The efficacy, safety, pharmacokinetic and immunogenicity of ALD403 will be assessed using the following endpoints. Greater detail concerning these endpoints can be found in Section 2.2.2.

Primary Efficacy Endpoint

• Change in frequency of migraine days (Weeks 1-12)

Key Secondary Efficacy Endpoints

- 75% migraine responder rate (Weeks 1-4)
- 75% migraine responder rate (Weeks 1-12)
- 50% migraine responder rate (Weeks 1-12)
- Percentage of subjects with a migraine on the day after dosing

Other Secondary Efficacy Endpoints

- Change in acute migraine medication days (Weeks 1-12)
- Headaches/Migraines with acute medication usage
- 100% migraine responder rates (Weeks 1-12)
- Short-Form Health Survey (SF-36 v 2.0)
- Health-Related Quality of Life (EQ-5D-5L)
- Allodynia Symptom Checklist-12 (ASC-12)
- Brush (dynamic mechanical) Allodynia
- Migraine responder rates for time periods other than Weeks 1-12
- Change in frequency of migraine days between baseline and time periods other than Weeks 1-12
- Headache responder rates
- Change in the frequency of headache days
- Percent change in headache/migraine days
- Time to first migraine after dosing
- Headache/Migraine hours
- Headache/migraines with severe intensity

Tertiary Endpoints

• Headache episodes/migraine attacks

Exploratory Endpoints

- Headache/Migraine characteristics
- Headaches/Migraines with type of acute medication usage
- Headache episode/Migraine attack average length

Safety Endpoints

- Adverse events (AEs) and serious adverse events (SAEs)
- Changes in clinical laboratory assessments
- Vital Signs
- ECGs
- Suicidal ideation and behavior as measured by the Columbia-Suicide Severity Rating Scale (C-SSRS)

Pharmacokinetic Endpoints

• Free ALD403 plasma concentrations

Immunogenicity Endpoints

- Development of specific anti-ALD403 antibodies
- Characterization of specific anti-ALD403 antibodies for neutralizing activity

2.2.1 eDiary

Subjects will complete a daily headache eDiary from the time of screening to Week 48. The diary is to be completed each trial day whether or not the subject had a headache. These daily entries record if the subject took acute migraine medication on that day.

The eDiary data from the 28 days following screening visit will be used to determine eligibility criteria, and the baseline migraine and headache results.

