2.5 Statistical Assessment of the Trial Objectives

Hypothesis testing will be performed for the primary endpoint: change from baseline in migraine days from Weeks 1-12. This endpoint will be calculated as outlined in Section 2.2.2 and will utilize the missing data rules provided in Section 2.7.2. The hypotheses tested are

$$H_o: \Delta_{plb} = \Delta_{403} H_a: \Delta_{plb} \neq \Delta_{403}$$

where Δ_{403} is the change in migraine days for subjects in the ALD403 treatment arm and Δ_{plb} is similarly defined for the placebo subjects. The change from baseline is expected to be negative as migraines are being reduced. While the test outlined above is two sided, as is the alpha level used for this study (i.e. 5%), clinically relevant results require a larger reduction of migraines on the ALD403 arms.

An ANCOVA model will be used to test for a difference between treatment arms. This model will include the change from baseline measure as the response variable. Treatment and the stratification variable: baseline migraine days (continuous covariate) will be the independent variables.

In addition, model based estimates including confidence intervals for the treatment differences will be used to summarize the results for the primary endpoint.

A sensitivity analysis of the change from baseline in migraine days will be performed using the sensitivity missing data rule provided in Section 2.7.2.

Secondary Efficacy Analyses

Summary statistics including confidence interval for the treatment differences will be used to summarize the results for the secondary endpoints. Testing will be performed for the key secondary endpoints and for the change in acute migraine medication days endpoint. For the key secondary endpoints (responder rates and percentage of subjects with a migraine on the day after dosing) this testing will utilize a CMH/extended CMH test. The tests will be stratified by the randomization stratification factor. The change in acute migraine medication day endpoints will be tested using an ANCOVA model similar to the one used for the primary endpoints: change from baseline measure as the response, treatment and baseline acute migraine medication days as independent variables. The time to first migraine analysis will be descriptively summarized based upon Kaplan-Meier methods.

Exploratory Analyses

Exploratory endpoints will be summarized with descriptive statistics by treatment group.

20

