3.4.2 Responder Rates

The responder rates will be determined as outlined in the missing data Section 2.7.2 and the endpoint definition in Section 2.2.2. The number of subjects who are responders and the rate (full analysis population as the denominator) will be summarized for each treatment group and at each 4, 12 and 24-week interval. The difference in rates and associated confidence interval will also be produced. These confidence intervals will be calculated based upon the normal approximation for two independent proportions. Stratification will not be used for these intervals. The SAS procedure, Proc Freq, will be used to calculate these confidence intervals. Any interval for which the normality assumption is questionable (i.e. np <5 or nq <5) will be flagged.

Plots of the percent of responders across time, for each response level, will be produced. These plots will use the four-week responder rates.

A p-value for the difference in rates for the key secondary endpoints will be based upon the CMH test outlined in Section 2.5. Significant p-values based on the formal decision rule criteria outlined in Section 2.7.5 will be clearly noted in the footnotes.

Should the as randomized and 'true' values for the stratification factors differ the as randomized values will be used within these CMH tests. The SAS procedure, Proc Freq, will be used to calculate this p-value.

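### Responder-rate intervals that fail the SAP's own small-count check are flagged but not replaced, which leaves the untested 100% responder comparison with a modestly under-covering interval

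*SAP*

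**What the plan says.** SAP 3.4.2 covers the 50%, 75% and 100% responder rates at each 4-, 12- and 24-week interval. Counts and rates come first: "The number of subjects who are responders and the rate (full analysis population as the denominator) will be summarized for each treatment group". The difference between groups then gets an unstratified interval: "These confidence intervals will be calculated based upon the normal approximation for two independent proportions". Proc Freq is the stated tool. The provision for small counts is: "Any interval for which the normality assumption is questionable (i.e. np <5 or nq <5) will be flagged". Section 3.4.2 names no score, exact or other interval to put in its place.

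SAP 2.2 lists "100% migraine responder rates (Weeks 1-12") among the other secondary endpoints, not the key ones. SAP 2.5 limits testing to the primary endpoint, the key secondary endpoints and acute migraine medication days. The key secondary responder rates are tested with a stratified CMH test.

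**The concern.** The plan sets its own criterion for when the method is doubtful and then prints the doubtful interval anyway. A flag warns readers off the interval but gives them nothing to use instead.

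The 100% responder rate over 12 or 24 weeks is where this is most likely to occur, because few placebo subjects may be free of migraine for that long. All three dose comparisons share the placebo arm, so a small placebo count flags all three at once. No p-value is planned for this endpoint, so the interval carries all of its inference. If the team reacted to a flagged interval by choosing another method, the choice would be made after unblinding.

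**Working it through.** **Inputs.** 200 per arm (SAP 1.5: "Two hundred subjects per group provides at least 95% power for each change in frequency of migraine days (Weeks 1-12) test individually"; "These subjects will be allocated into 4 treatment groups in a 1:1:1:1 ratio"). SAP 3.4.2 states no confidence level; 95% is assumed, to match the two-sided 5% alpha in SAP 2.5. No continuity correction is assumed, and p in the flag rule is taken as the observed rate. No document gives a planning rate for 100% response. The only 100% responder rates anywhere are 16% vs 0% over 12 weeks, in the superseded column of Protocol 15.6. They come from an earlier single-dose 1000 mg study, so they are context and not a planning value.

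**The plan's own figures.** It states no coverage. Its responder power claims do reproduce at n = 200, using Φ{[d√n − 1.96√(2p̄q̄)] / √(p1q1 + p2q2)}:
- 24% vs 42%: (2.546 − 1.303)/0.653 = 1.90, power 97.1%.
- 50% vs 68%: (2.546 − 1.363)/0.684 = 1.73, power 95.8%.

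Both meet the stated 95%.

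**The flag.** np < 5 with n = 200 means x ≤ 4, an observed rate below 5/200 = 2.5%. With ALD403 at 5-16%, the probability of a flag is 1.00 at a true placebo rate of 0%, above 0.99 at 0.5%, about 0.95 at 1% and about 0.63 at 2%.

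**The planned interval.** d ± 1.96√(p1q1/n + p2q2/n). An arm with no responders adds nothing to the variance.
- 32/200 vs 0/200: 0.16 ± 1.96√(0.16 × 0.84/200) = 0.16 ± 0.0508, that is 10.9% to 21.1%.
- 0/200 vs 0/200: [0, 0].

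**A Newcombe interval.** It combines the Wilson limits (l, u) of the two arms: lower d − √[(p1 − l1)² + (u2 − p2)²], upper d + √[(u1 − p1)² + (p2 − l2)²]. For 0/200 the Wilson upper limit is 3.84/203.84 = 1.9%.
- 32/200 vs 0/200: 11.2% to 21.7%.
- 0/200 vs 0/200: −1.9% to +1.9%.

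**Exact coverage.** The joint binomial probabilities were summed over all 201 × 201 outcomes. All rates are assumed.

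| ALD403 vs placebo | Normal approx. coverage | Upper limit too low | Lower limit too high | Newcombe coverage |
|---|---|---|---|---|
| 16% vs 0% | 93.8% | 4.6% | 1.6% | 95.8% |
| 10% vs 0% | 92.7% | 5.7% | 1.6% | 96.7% |
| 5% vs 0% | 92.6% | 6.2% | 1.2% | 97.9% |
| 10% vs 0.5% | 94.4% | 4.2% | 1.5% | 96.3% |
| 10% vs 1% | 94.2% | 4.1% | 1.7% | 95.5% |
| 10% vs 2% | 94.8% | 3.6% | 1.6% | 95.7% |
| 2% vs 0.5% | 89.9% | 9.2% | 0.8% | 97.4% |
| 1% vs 0.5% | 85.9% | 13.5% | 0.6% | 99.1% |
| 1% vs 0.1% | 86.3% | 13.4% | 0.4% | 99.9% |
| 1% vs 1% | 96.0% | 2.0% | 2.0% | 98.4% |
| 42% vs 24% | 94.8% | 2.4% | 2.7% | 95.0% |
| 68% vs 50% | 94.9% | 2.3% | 2.7% | 94.9% |

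With ALD403 stepped by half a point from 5% to 16%, and placebo between 0% and 2%, coverage of the planned interval runs from 92.0% to 95.4%. The average is 94.0% at placebo 0% and 94.6% at placebo 2%. Upper limits below the true difference make up 64-91% of the misses. Because the counts are discrete, there are isolated dips when placebo is exactly 0%, such as 90.6% at 5.4% and 88.6% at 3.25%.

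When both arms are very low, coverage is erratic and not bounded by 86%: 80.0% at 1.5% vs 0% and 63.2% at 0.5% vs 0%, but 98.6% at 0.5% vs 0.5%.

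**The case against.** The strongest reply is that little depends on these intervals. The 100% responder rate is outside the testing sequence, the key secondary p-values come from CMH tests, and the 50% and 75% intervals are near nominal at the planning rates with essentially no chance of a flag. The plan also discloses the weakness, and it reports counts and denominators from which a reader could compute a score interval. At 32/200 vs 0/200 the two intervals are practically the same. All of this stands, and it limits the point to a minor reporting improvement. It does not supply a usable interval where the flag fires.

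Three stronger readings are tempting, and the documents do not support them:

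- **That 100% responder intervals will cover only about 86%.** That needs about 1% or less in both arms, and no document suggests such rates on ALD403. The only rates shown give 93.8%.
- **That the errors fall almost wholly on one side.** This is so at 1% vs 0.1% (13.4% against 0.4%), but at 16% vs 0% the split is 4.6% to 1.6%. In the unequal low-rate cases the heavier miss understates the difference, so a false claim of benefit is not the main risk.
- **That no placebo responders gives an interval of zero width.** SAP 3.4.2 plans an interval only for the difference, and that interval vanishes only when both arms are at 0% or 100%.

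**Conclusion.** The point holds as a minor one. SAP 3.4.2 recognises when its interval is unreliable and names nothing to replace it, and the endpoint most exposed has no test behind it.

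Under the assumptions above, the loss is about 0 to 3 percentage points of coverage for ALD403 rates of 5-16% and placebo rates of 0-2%. Coverage of 86-90% generally requires both arms at about 2% or less, apart from isolated dips when placebo is exactly zero.

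These figures belong to the assumed rates and are not a property of the plan. A continuity correction, on which SAP 3.4.2 is silent, would change some of them: 96.1% at 16% vs 0%, but still 86.6% at 1% vs 0%. No primary or key secondary conclusion is affected.

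**What to change.** In SAP 3.4.2, state that any responder-rate comparison meeting the np < 5 or nq < 5 criterion will be reported with a score interval for the risk difference instead of the flagged normal-approximation interval. Name one method in advance, Newcombe or Miettinen-Nurminen. State the confidence level in the same sentence. Using the score interval for all responder-rate differences is also acceptable. It avoids switching method on the observed counts, and at the 50% and 75% planning rates Newcombe coverage is 94.9-95.0%, so nothing is lost there.

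The cost is one SAP sentence and one Proc Freq option. The drawback is conservatism when both rates are very low: Newcombe covers up to 99.9% at 1% vs 0.1%. Miettinen-Nurminen coverage was not computed here.

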3.4.3.1 Percentage of Subjects with a Migraine on the Day after Dosing

The missing data rules provided in Section 2.7.2 will be used for the key secondary endpoints except for the percentage of subjects with a migraine (prevalence) on the day after dosing endpoint. Subjects who did not complete the eDiary on the day following dosing will be included in to the prevalence rate calculation based upon their month 1 daily migraine rate. Hence, subjects with a migraine will be included in the rate calculation as a value of 1, subjects who completed the diary and did not have a migraine will be included as a zero and subjects who did not complete the diary will be included with a value between 0 and 1 equal to the number of month 1 migraine days / 28.

The percentage of subjects with a migraine (full analysis population as the denominator) will be summarized for each treatment group at baseline and each day from Day 0 to Day 7. A p-value for the difference from Placebo in the percentage of subjects with a migraine on the day after dosing (Day 1) key secondary endpoint will be based upon the extended CMH test stratified by the randomization stratification factor. Significant p-values based on the formal decision rule criteria outlined in Section 2.7.5 will be clearly noted in the footnotes.

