9.3 Investigational Product Dosing and Administration

The pharmacist or Investigational Product consignee responsible for dispensing and preparing the ALD403 and Placebo IV infusions will be unblinded and will not be responsible for other aspects of the clinical trial where blinding is necessary. The infusions will be prepared using aseptic techniques.

The doses of ALD403 or Placebo (total volume of 100 mL) will be administered IV over a period of 1 hour (± 15 minutes) on Day 0 and Week 12, 24 and 36, by the blinded Investigator or designee. Subjects must be monitored for 4 hours after the dosing completion. If the subject experiences a headache or migraine on dosing day, dosing may occur if it doesn't compromise the safety of the subject in the judgment of the Investigator.

Further instructions on the preparation and procedure associated with administering the IV can be found in the Pharmacy Manual.

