2.2.2 Migraine and Headache Endpoints

In the statistical analysis plan the term headache will encompass both headaches and migraine headaches. Migraine headaches (migraines) are a subgroup of the headaches with the characteristics outlined below. In this way all migraines are headaches but not all headaches are migraines. Migraine and headache data will be collected through week 48. Headache episodes will be self-reported by the subject. An episode is a single headache event which lasts at least 30 minutes, as defined by the subject reported start and end time. The migraine and headache endpoints will be summarized in four week, twelve week and the twenty-four week intervals. Specifically, migraine and headache endpoints will be summarized for the four week intervals: Weeks 1-4, 5-8, 9-12, 13-16, 17-20, 21-24, ... 44-48, the twelve week intervals 1-12, 13-24, 25-36, 37-48, and Weeks 1-24, 25-48 as outlined in Section 2.3. The results from Weeks 1 to 12 will be used for the primary analysis.

For this trial, migraines are defined using the definition of migraine without aura and probable migraine without aura as outlined by the International Headache Society. These definitions do not take the presence of aura into account. Subjects will report if they experienced aura with their headache. Hence, in the rare case of aura that does not develop into a migraine, this will not be classified as a migraine but a headache that meets the definition of a migraine without aura will be considered a migraine regardless of if aura was present or not.

Migraine Day

A migraine day is defined as any day with a headache that meets the migraine or probable migraine characteristics as outlined in the International Headache Society (IHS), ICHD II 2004-II, Section 1.1 and 1.6. Specifically, a migraine is defined as a self-reported headache that:

- 1. Lasted 4-72 hours
- 2. Had at least 2 of the following
 - a. Unilateral location
 - b. Pulsating quality
 - c. Moderate or severe pain intensity
 - d. Aggravation by or causing avoidance of routine physical activity

3. Had at least 1 of the following

- a. Nausea and/or vomiting
- b. Photophobia and phonophobia

A probable migraine is a headache that meets only 2 of the above criteria. These characteristics will be summarized for each 4-week interval.

Frequency, Change and Percent Change of Migraine Days / Headache Days

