2.7.5 Multiple Comparisons/Multiplicity

A serial procedure will be used to account for multiplicity of dose level for the primary endpoint and the secondary endpoints. This procedure will start with the 300 mg vs placebo comparison for the primary endpoint. If this is significant, testing will continue to a subset of the key secondary endpoints for 300 mg (first the Weeks 1-4 75% responder endpoint, then the Weeks 1-12 75% responder endpoint, and then the Weeks 1-12 50% responder endpoint). The procedure will then move on to the primary endpoint for the 100 mg group and subsequently to the same subset of key secondary endpoints as tested for the 300 mg dose. The procedure will then move on to the remaining key secondary endpoint for 300 mg and 100 mg (i.e., percentage of subjects with a migraine on the day after dosing). Only if all of these secondary endpoints reach statistical significance will the 30 mg group be tested.

Statistical testing will be conducted at the 5% alpha level.

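### The Day 1 migraine test leaves a pre-dose headache status from the eDiary unused; adjusting for it is a free but small gain in precision

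*SAP*

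**What the plan says.** SAP 2.2.2 defines the endpoint as the percentage of subjects with a migraine on the day after the first dose, and SAP 3.4.3.1 calls it a prevalence. Neither place requires the attack to have begun after the infusion. In SAP 2.2.2, "A migraine day is defined as any day with a headache that meets the migraine or probable migraine characteristics"; a migraine lasts 4 to 72 hours, and one attack can give several migraine days. Protocol 9.3 foresees infusion during an attack: "If the subject experiences a headache or migraine on dosing day, dosing may occur if it doesn't compromise the safety of the subject", in the investigator's judgment.

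On the test, SAP 3.4.3.1 says that the p-value for this "key secondary endpoint will be based upon the extended CMH test stratified by the randomization stratification factor". By SAP 1.3 that factor is screening-period migraine days, ≤9 vs >9. SAP 3.4.3.1 also tabulates migraine prevalence at baseline and on each day from Day 0 to Day 7, but the test does not use these figures.

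In the serial procedure of SAP 2.7.5 the Day 1 tests for 300 mg and 100 mg come last before the low dose: "Only if all of these secondary endpoints reach statistical significance will the 30 mg group be tested".

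**The concern.** A subject who is in an attack when the infusion starts is plausibly more likely to have a migraine the next day than a subject who is not. The randomization factor describes how often a subject has migraines over 28 days. It says little about whether one was under way at dosing. If pre-dose status predicts Day 1 status, leaving it out of the test leaves avoidable variation in the comparison.

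Two Day 1 tests must succeed before the 30 mg arm can be tested at all, so any power lost here is also lost to that arm. The information is already collected: the eDiary runs daily from screening, with headache start and end times.

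**Working it through.** **Inputs from the documents.** Alpha: "Statistical testing will be conducted at the 5% alpha level", and SAP 2.5 makes it two-sided ("While the test outlined above is two sided, as is the alpha level used for this study"). Size: "Two hundred subjects per group", "allocated into 4 treatment groups in a 1:1:1:1 ratio" (SAP 1.5). Assumed Day 1 rates: 15% placebo, 4% ALD403, stated power 95% (SAP 1.5).

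**Step 1: the plan's figure.** Power = Φ{(|p₁−p₂| − 1.96·SE₀)/SE₁}.
- SE₀ = √(2 × 0.095 × 0.905/200) = 0.02932
- SE₁ = √{(0.15 × 0.85 + 0.04 × 0.96)/200} = 0.02880
- Power = Φ{(0.11 − 0.0575)/0.0288} = Φ(1.82) = 96.6%
- With a continuity correction (0.11 − 0.005 in place of 0.11): Φ(1.65) = 95.1%

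The stated 95% reproduces. The 300 mg and 100 mg tests share the placebo arm, so their correlation is 0.1275/(0.1275 + 0.0384) = 0.77. The chance that both pass is then 94.6%.

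**Step 2: gain if the drug acts equally on running and new attacks.** Simulation of 10,000 trials, 200 per arm, comparing CMH stratified by ≤9 / >9 with CMH stratified by that factor crossed with pre-dose migraine (yes/no). Assumptions not in the documents: mean baseline 8.24 migraine days, 32% of subjects above 9 days, chance of a pre-dose migraine equal to days/28 (8.24/28 = 29% on average), the same relative effect in both pre-dose groups, and placebo Day 1 risk 1, 2, 3 or 5 times higher after a pre-dose migraine.

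| Rates | Risk ratio | One test: plan → adjusted | Both tests: plan → adjusted |
|---|---|---|---|
| 15% vs 4% | 1 | 97.8% → 97.7% | 95.7% → 95.6% |
| | 2 | 97.7% → 97.8% | 95.5% → 95.9% |
| | 3 | 97.7% → 97.9% | 95.6% → 96.2% |
| | 5 | 97.8% → 98.6% | 95.9% → 97.3% |
| 15% vs 7% | 2 to 5 | 74% → 74-78% | 61-62% → 61-66% |
| 25% vs 15% | 2 to 5 | 72-73% → 73-81% | 58-60% → 60-70% |

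The first four rows are the plan's own rates. The last two are assumed weaker effects.

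**Step 3: gain if carried-over attacks are not shortened.** Let a share q be in an attack at infusion, r of those attacks reach Day 1 in every arm, and u be the new-onset risk (assumed 10% placebo, 3% active). With c = q·r, the Day 1 rate is c + (1 − c)u.

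| q, r | c | Placebo | Active | One test: without → with flag | Both tests |
|---|---|---|---|---|---|
| 5%, 30% | 1.5% | 11.4% | 4.5% | 74% → 77% | 61% → 65% |
| 15%, 30% | 4.5% | 14.1% | 7.4% | 58% → 64% | 42% → 49% |
| 15%, 50% | 7.5% | 16.8% | 10.3% | 47% → 59% | 31% → 43% |

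These runs (20,000 trials) compare an unstratified CMH with one stratified on attack status. Repeating the last two rows with the plan's ≤9 / >9 strata as the comparator gave 59% → 65% and 48% → 60%, so the gain is not an artefact of dropping the planned stratum. At 15% vs 4% the same repeat gave about 97.9% → 98.4%. With no treatment effect, rejection was 5.0% without and 4.7% with the flag.

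**The case against.** A reader might infer three stronger things. The documents support none of them.

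*The endpoint is mis-scored.* It is defined as a prevalence, so counting a running attack follows the definition. Ending such an attack would be a benefit that the endpoint rightly credits. Nothing in either document calls it a new-onset endpoint.

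*The comparison is biased.* Pre-dose status precedes randomization and is balanced in expectation, and the null rejection rates above are nominal.

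*The test is badly underpowered and blocks the 30 mg arm.* The 47-58% starting powers come mainly from an assumed weaker effect. The active rates there are 7.4% and 10.3%, against the plan's 4%. With 15% in attack and 30% carry-over, c alone is 4.5%, so 15% vs 4% cannot occur under that model. This cuts both ways: the plan's high power is no reassurance if carry-over of that size is real. The documents do not settle which case applies.

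Other objections stand in part. Nothing shows that pre-dose status is the strongest predictor. The planned Day 0 to Day 7 table and the time-to-first-migraine analysis (SAP 3.4.3.2) already give related descriptive information. A flag for a headache ongoing at infusion would not be clean either. SAP 2.7.2 sets a missing headache end from the next reported headache or the last diary entry, so post-dose data could enter the stratum. That is a reason to choose a simpler flag; it does not remove the case for adjusting.

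**Conclusion.** The point holds as a minor, free improvement in precision. At 15% vs 4%, adjusting is worth about 1 point or less per test and about 0 to 2 points on the joint 300 mg and 100 mg gate. If running attacks are not shortened, or the true effect is weaker, it is worth roughly 3 to 12 points per test under the assumed 5-15% in attack and 30-50% carry-over. It is near zero if few attacks carry over.

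The 3 to 12 points were computed with true attack status at infusion. A Day -1 flag is a proxy for it and would recover less if it predicts less well. The simulations also did not model the fractional values that SAP 3.4.3.1 assigns to missing Day 1 diaries.

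**What to change.** In SAP 3.4.3.1 and 2.5, stratify the Day 1 extended CMH test by the randomization factor crossed with one flag, defined in the same way for every subject: headache recorded in the eDiary on Day -1 (yes/no).

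- Use only entries made before the infusion. Do not use imputed or post-dose end times, and do not mix the flag with a variable based on infusion time.
- Any headache is the cleaner choice over migraine. By SAP 2.7.2 the questions that classify a headache go unanswered until the subject reports its end, which may be after dosing.
- No headache recorded on Day -1 counts as no, so a missing entry needs no imputation.
- Leave the endpoint definition unchanged. Optionally report, as supportive, Day 1 migraine with onset after the infusion began.

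The cost is SAP wording, one derived flag and four strata instead of two. The strata should not be too sparse. Under the Step 2 assumptions 10, 8, 6, 5 and 3% of subjects have 10, 11, 12, 13 and 14 baseline days, a mean of 367/32 = 11.5 days. The smallest stratum is then about 200 × 0.32 × 11.5/28 ≈ 26 per arm.
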